## 6 STUDY DRUG/MEDICATION MANAGEMENT

### 6.1 Description of Study Drug/Medication

#### 6.1.1 *Investigational Product*

An investigational product, also known as investigational medicinal product in some regions, is defined as follows:

A pharmaceutical form of an active substance or placebo being tested or used as a reference in a clinical study, including products already with a marketing authorization but used or assembled (formulated or packaged) in a way different from the authorized form, or used for an unauthorized indication, or when used to gain further information about the authorized form.

- The investigational product should be stored in a secure area according to the local regulations. It is the responsibility of the investigator to ensure that the investigational product is only dispensed to study patients. The investigational product must be dispensed only from official study sites by authorized personnel according to local regulations.
- During the Double-Blind Treatment Phase, investigational product (study drug/medication) is rimegepant (BHV-3000) 75 mg Immediate Release (IR) Tablet or matching placebo dosed daily.
- During the Open-label Extension Phase, investigational product (study drug/medication) is rimegepant (BHV-3000) 75 mg orally disintegrating tablet (ODT) dosed daily.
- All subjects, regardless of the treatment phase, will take study drug/medication daily.

**NOTE:** During the Double-blind and Open-label Extension Phase, if a dose of study drug/medication for a given day is missed, lost, or otherwise unable to be taken, the subject should document that as a missed dose on the **subject paper study log**.

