### **6.2.3 Dose Modifications**

There will be no dose adjustments in this study.

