During the DBT Phase of the study, subjects will be randomized to a sequence of either rimegepant (75 mg QD) and then placebo or placebo then rimegepant (75 mg QD) in a 2-sequence, 2-period, crossover design. Study drug/medication will be dispensed at the baseline visit and at Days 14 and 21. Subjects should take the first dose the day of the baseline visit. Study drug/medication should be administered in the morning without regard to meals. Subjects who showed continued compliance during the DBT Phase may choose to enter a 12 week OLE Phase with daily dosing of rimegepant (75 mg QD) ODT. Open label study drug will be dispensed at the Day 35 visit for subjects who enter the OLE Phase. Subjects should take the first dose of OLE study drug on Day 36.

Subjects report study drug exposure in the subject paper study log (diary), whereas sites report study drug accountability on the Study Drug Dispensing Log CRF.

An administrative listing of IP batch numbers is provided for the treated analysis set. Refer to the Core SAP for listing contents.

DB Study Drug (Rimegepant or Placebo) Exposure

DB rimegepant or placebo exposure will be summarized descriptively by as-treated treatment groups for period 1 placebo, period 1 rimegepant, period 2 rimegepant, period 2 placebo, rimegepant pooled, placebo pooled and overall, and will include the following parameters:

- Time on DBT (days), derived as DBT end date – DBT start date + 1
- Time on DBT study drug category (weeks)
- Cumulative DBT exposure (mg), derived by summing number of DB mg across DB study drug records
- Average DBT exposure (mg per day), derived as cumulative DB exposure/time on DBT
- Total DBT exposure (tablets) summed across all subjects, derived by summing cumulative DB exposure across all subjects.
- Total DBT exposure (patient-years), derived by summing (DBT end date – DBT start date + 1)/365.25 across all subjects.

OL Rimegepant Exposure

OL rimegepant exposure will be summarized descriptively by treatment sequence and overall, and will include the following parameters:

- Time on OL rimegepant (days), derived as OL rimegepant end date – OL rimegepant start date + 1
- Time on OL rimegepant category (weeks)
- Cumulative OL rimegepant exposure (mg), derived by summing number of OL mg across records with non-missing OL rimegepant date/times.
- Average OL rimegepant exposure (mg per day), derived as cumulative OL rimegepant exposure/time on OL rimegepant

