- Total OL rimegepant exposure (tablets) summed across all subjects, derived by summing cumulative OL rimegepant exposure across all subjects
- Total OL rimegepant exposure (patient-years), derived by summing (OL rimegepant end date – OL rimegepant start date + 1)/365.25 across all subjects.

DB or OL Rimegepant Exposure

DB or OL rimegepant exposure will be summarized descriptively by as-treated DB rimegepant pooled/OL rimegepant, DB placebo pooled/OL rimegepant and overall, and will include the following parameters:

- Time on DB or OL rimegepant (days), derived as DB or OL rimegepant end date – DB or OL rimegepant start date + 1
- Time on DB or OL study drug category (weeks)
- Cumulative DB or OL rimegepant exposure (mg), derived by summing number of DB or OL mg across records with non-missing DB or OL rimegepant date/times.
- Average DB or OL rimegepant exposure (mg per day), derived as cumulative DB or OL rimegepant exposure/time on DB or OL rimegepant.

- Total DB or OL rimegepant exposure (tablets) summed across all subjects, derived by summing cumulative DB or OL rimegepant exposure across all subjects. Total DB or OL rimegepant exposure includes missed dose days within a study phase and excludes the dosing break between study phases (i.e., (last dose day of DB study drug – first dose date of DB study drug + 1) – (number of days with a dosing break between the DB and OL phases)).
- Total DB or OL rimegepant exposure (patient-years), derived by summing (DB or OL rimegepant end date – DB or OL rimegepant start date + 1)/365.25 across all subjects.

A by-subject listing of study drug exposure will be provided for the treated analysis set.

6.2.6.2 *Drug Accountability and Compliance*

DB study drug accountability and compliance will be tabulated by as-treated treatment groups for period 1 placebo, period 1 rimegepant, period 2 rimegepant, period 2 placebo, rimegepant pooled, placebo pooled, and overall with the number and percentage of subjects in the following categories for the DB phase:

- Any bottle dispensed (Yes, No, Not Reported)
- DB study drug taken but not randomized
- Tablet count compliance < 80% from study drug start to study drug end in DB phase
- More than the required number of tablets administered on 1 day
- Did not return ≥ 1 bottle dispensed and discontinued study drug, defined as any of the following:
 - Randomized subjects who were not treated and did not return DB bottle dispensed

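### SAP 6.2.6.1 labels total exposure in tablets but derives it by summing milligrams: the DB and OL rimegepant totals come out 75 times the tablets taken, and the placebo total is undefined

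*SAP*

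**What the plan says.** SAP 6.2.6.1 (Study Therapy) lists exposure parameters in three blocks: double-blind (DB), open-label (OL), and DB or OL rimegepant combined.

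In the DB block, cumulative exposure is "Cumulative DBT exposure (mg), derived by summing number of DB mg across DB study drug records". The next derivation is "Average DBT exposure (mg per day), derived as cumulative DB exposure/time on DBT". Then comes "Total DBT exposure (tablets) summed across all subjects, derived by summing cumulative DB exposure across all subjects".

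The OL block has the same structure and ends with "Total OL rimegepant exposure (tablets) summed across all subjects, derived by summing cumulative OL rimegepant exposure across all subjects". The combined block has "Total DB or OL rimegepant exposure (tablets) summed across all subjects, derived by summing cumulative DB or OL rimegepant exposure across all subjects". It then adds that this total counts missed-dose days within a phase and leaves out the break between phases, with a formula made of date differences.

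The DB rows are not for active drug alone: "DB rimegepant or placebo exposure will be summarized descriptively by as-treated treatment groups", with columns for each treatment by period, each treatment pooled, and overall.

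On dose, Protocol 6.1.1 describes the double-blind product as "rimegepant (BHV-3000) 75 mg Immediate Release (IR) Tablet or matching placebo dosed daily" and the open-label product as a 75 mg ODT once daily. Protocol 6.2.3 says "There will be no dose adjustments in this study".

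**The concern.** A row headed tablets should count tablets. Here each block takes a quantity that it has just defined in mg and adds it over subjects. No step divides by tablet strength or counts tablets, and the pattern appears three times, so this is not an isolated slip of the pen.

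SAP 6.2.6 says that the exposure analyses support the safety evaluation. If the rule is followed, the report would show a rimegepant tablet total far above the tablets swallowed. Beside it would stand a placebo total whose value depends on a coding choice that the SAP does not state. Two programmers could produce different tables from the same text, one following the label and the other the derivation.

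**Working it through.** The documents state no exposure total, so there is no figure to reproduce. The check is one of units.

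**Inputs**
- Cumulative exposure is in mg (SAP 6.2.6.1). The mg-per-day row confirms this: cumulative exposure divided by days gives mg per day only if the numerator is in mg.
- Every rimegepant tablet is 75 mg in both phases, with no dose adjustment (Protocol 6.1.1, 6.2.3).
- Dosing is once daily. Each treatment period lasts 14 days, with a 7-day placebo washout between them (SAP 2.1). The extension runs from Day 36 to Day 119 (Protocol 3.5.4).

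**1. Rimegepant, DB and OL blocks.** If subject i takes T_i tablets, cumulative exposure is 75 × T_i mg. The row is then Σ(75 × T_i) = 75 × ΣT_i. Its ratio to tablets taken is 75, whatever the enrolment, adherence or duration. For one fully adherent subject:
- DB: 14 tablets; 14 × 75 = 1,050 shown.
- OL: 119 − 36 + 1 = 84 tablets; 84 × 75 = 6,300 shown.

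**2. Placebo, DB block.** The SAP gives no mg value for a placebo tablet, and 6.2.6.1 does not say whether washout tablets are counted as placebo exposure. For one fully adherent subject:

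| Washout tablets | Placebo tablets taken | Shown if placebo is 0 mg | Shown if placebo is a nominal 75 mg |
|---|---|---|---|
| Not counted | 14 | 0 | 14 × 75 = 1,050 |
| Counted | 14 + 7 = 21 | 0 | 21 × 75 = 1,575 |

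No cell in the last two columns is a tablet count.

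**3. Overall, DB block.** With placebo at 0 mg, the row shows 1,050 against 14 + 14 = 28 tablets without the washout (1,050 / 28 = 37.5 times), or against 35 tablets with it (1,050 / 35 = 30 times). With placebo at a nominal 75 mg, the ratio is 75.

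**4. Combined block.** Let D be the dosing days and a the share of doses taken. Tablets taken are aD, the summing rule gives 75aD, and a day count that includes missed doses gives D. For illustration, take a = 0.8, the level below which Protocol 6.4 calls compliance poor. The three results are 0.8D, 60D and D. The summing rule is 75 times the tablet count, and the day count is 1 / 0.8 = 1.25 times it. One row thus has a tablet label, an mg derivation and a day-count explanation, and no single factor describes the error.

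**5. What does not depend on the row.** Time on drug and patient-years are derived from dates. Cumulative mg and mg per day for rimegepant are in their proper units. Exposure-adjusted AEs use reference start and end dates (SAP 6.4.1.3, 6.4.1.5). Tablet-count compliance is a separate item (SAP 6.2.6.2). No efficacy model uses exposure.

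**The case against.** The strongest reply is that the documents show only a label and a derivation that disagree. If the word tablets is the slip and a total in mg was meant, the rimegepant sum is a correct mg total and nothing is inflated. That is fair: the text does not say which was intended, and the mock tables and Core SAP were not available for this review. But the row is wrong as printed under either intention. The Core SAP does not settle it either. Under SAP Section 1 it governs where this SAP is silent or refers to it, and here this SAP gives its own derivation.

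A second reply is that a reviewer would notice 1,050 tablets beside 14 days on drug. Probably so, but correcting it would mean departing from the SAP without a stated rule.

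A reader might also infer more than the documents support:
- **A factor of 75 in all three tables.** It is established for the DB and OL rimegepant rows. In the combined block the day-count sentence defines a different quantity.
- **A study total of 63,000 in place of 840 (60 × 14).** That takes all 60 randomized patients as completers. The sample-size section assumes 20% dropout (60 × 0.8 = 48), and SAP Section 1 records early termination for low enrolment. The ratio holds; those totals do not.
- **Equal rimegepant and placebo tablet totals once corrected.** If washout tablets count as placebo, a completer has 21 placebo tablets against 14 of rimegepant.
- **Distorted safety conclusions.** No safety rate or denominator uses the tablet total.

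**Conclusion.** The point holds as a unit error in a stated derivation. Programmed literally, the DB and OL rimegepant tablet totals are exactly 75 times the tablets taken. The DB placebo total is undefined: 0 or 75 times too high. The DB overall total inherits that ambiguity. The combined row mixes three units.

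The factor rests on the single 75 mg strength, the absence of dose adjustment, and the text being followed as written. The per-subject figures also assume full adherence.

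The reach is small: one descriptive row in each of three exposure tables. It is still worth correcting, because SAP Section 8 says that all analyses described in the SAP are included in the report.

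**What to change.** 1. In all three blocks, derive total exposure (tablets) as the sum of tablets recorded as taken, for placebo as well as rimegepant where both are shown. If a total in mg was intended, relabel the row as mg and report it for rimegepant only.
2. In the combined block, remove the day-count sentence from the tablet row, or move it to a row in days or patient-years. If it moves, make it agree with that row's derivation: the patient-years formula as printed does not subtract the break between phases.
3. State whether washout placebo tablets count in the placebo and overall DB totals.

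The cost is three derivation lines, one sentence on the washout, and the matching table shells. No new data are needed: subjects record each tablet in the paper diary (Protocol Table 1, footnote f), and SAP 6.2.6.2 already uses tablet counts for compliance.

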6.3 Efficacy

Unless otherwise noted, the primary and secondary efficacy analyses will be conducted on the mITT population. DBT and OLE efficacy data will be included in listings by subject, treatment sequence and period, study phase and visit (as applicable). Descriptive summary statistics will be provided for DBT and OLE phase data. Statistical analyses outlined in Table 3: Primary and Secondary Efficacy Estimands and Analyses will only be done for the DBT phase data.

Table 3: Primary and Secondary Efficacy Estimands and Analyses

Index	Description	Variable Type	Statistical Model	On-Study Data
Primary Estimand				
P01	Difference between treatment groups in change from baseline in average daily NPRS scores at the end of the randomization phase	Continuous	MMRM	Baseline, Day 14, 21, 35
Secondary Estimand				
S01	Difference between treatment groups in change from baseline in Penn-FPS-R score at the end of the randomization phase	Continuous	MMRM	Baseline, Day 14, 21, 35
S02	Difference between treatment groups in change from baseline in Pain Disability Index at the end of the randomization phase	Continuous	MMRM	Baseline, Day 14, 21, 35
S03	Difference between treatment groups in PGI-C at the end of the randomization phase	Continuous	MMRM	Day 14, 21, 35
S04	Difference between treatment groups in change from baseline in worst pain episode measured by NPRS at the end of the randomization phase	Continuous	MMRM	Baseline, Day 14, 21, 35
S05	Difference between treatment groups in percentages of subjects with ≥ 2 point reduction from baseline in average daily NPRS score	Binary	Logistic Regression	Baseline, Day 14, 21, 35

MMRM = Mixed effects model for repeated measures

6.3.1 *Continuous Efficacy Endpoints*

Assessments are taken directly from reported CRF visits, aside from the NPRS endpoints which are only taken between treatment exposure start and end dates.

Descriptive Analyses

Summary statistics for parameter values are tabulated at select time points by treatment group (rimegepant pooled or placebo pooled).

MMRM

Treatment groups are assessed using MMRM with the following variables:

- Dependent variable: change from baseline of NPRS score averaged over each DBT period
- Fixed effects (categorical variables): treatment group, sequence, and period
- Covariate (continuous variable): baseline value of dependent variable

Random effect: subject error degrees of freedom are determined by the Kenward-Roger method.

The following statistics are tabulated from the MMRM:

- Least-squares mean (LSMean) with corresponding SE with 95% confidence intervals (CIs) of changes from baseline by treatment group (pooled rimegepant, pooled placebo).
- Difference in LSMeans between treatment groups (pooled rimegepant, pooled placebo) with corresponding SE, and 95% CI.

6.3.2 *Continuous Efficacy Endpoints without Baseline Measurement*

Assessments are taken directly from reported CRF visits.

Descriptive Analyses

Descriptive statistics will be presented at select time points by treatment group (rimegepant pooled or placebo pooled).

MMRM

Treatment groups are assessed using MMRM with the following variables:

- Dependent variable, e.g., PGI-C score at Day 14 (note that Day is relative to the start of each treatment period)
- Fixed effects (categorical variables): treatment group, sequence, and period
- Random effect: subject error degrees of freedom are determined by the Kenward-Roger method.

The following statistics are tabulated from the MMRM:

- LSMean with corresponding standard error (SE) with 95% CIs of values by treatment group
- Difference in LSMeans between treatment groups (rimegepant, placebo) with corresponding SE, and 95% CI.

6.3.3 *Binary Efficacy Endpoints*

Assessments are taken directly from reported CRF visits, aside from the NPRS endpoints which are only taken between treatment exposure start and end dates.

Descriptive Analyses

Descriptive statistics will be presented at select time points by treatment group (rimegepant pooled or placebo pooled).

Logistic Regression

Treatment groups are assessed using Logistic Regression with the following variables:

- Dependent variable, e.g., \geq 2-point reduction in average daily NPRS score
- Fixed effects (categorical variables): treatment group, sequence, and period
- Covariate (continuous variable): baseline value of NPRS

The following statistics are tabulated from the logistic regression:

- Number and percentage of subjects with \geq 2-point reduction in average NPRS score by treatment group
- Observed percentage difference (rimegepant vs. placebo)
- Odds ratio between rimegepant and placebo with corresponding 95% CI.

6.3.4 *P01: Primary Efficacy Endpoint: NPRS*

6.3.4.1 *Main Analyses*

The NPRS is a segmented, 11-item, numeric scale ranging from 0-10. The NPRS is anchored by items ranging from “0” which represents “no pain;” to “10” which reflects “worst pain imaginable.”

Subjects were given a paper diary to record daily pain intensity on the NPRS. They were asked to keep a daily record of their average pain intensity over a 24 hour period.

The primary endpoint is the change in average daily NPRS from baseline to the end of the 2-week treatment phase of the study. Pain relief is defined as an improvement (reduction) from baseline. The primary endpoint will estimate the effect of rimegepant relative to placebo over 2 weeks of treatment when added to a standard of care therapy, and regardless of the effect of other concomitant medication. The pain score will be the average of the daily 11-point NPRS recorded within each period using the mITT population. This treatment effect will be

summarized as the difference in the average daily score in total NPRS between rimegepant and placebo.

The primary endpoint will be analyzed using the method specified in Section 6.3.1. The MMRM table has the same format as the one described in Section 6.3.1.

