### **3.5.2      Randomization Phase (35 Days)**

Patients with a mean score of greater than or equal to 4 on the daily “average intensity” 11 point Numeric Pain Rating Scale, during the 14 to 30 day screening period, will be randomized to one of two treatment sequences to receive BHV-3000 (75 mg QD) administered orally vs placebo (QD) in a 1:1 ratio. Patients should be encouraged to take their dose of medication in the mornings. Patients with a diagnosis of typical and atypical TN will be stratified equally into the two sequences; and patients with atypical TN will not exceed 50% of the subjects. Each sequence will include a 2 week treatment phase, with daily dosing of study drug/medication or placebo. This will be followed by a 7 day placebo washout period. After the placebo washout period, another 2 week treatment phase will follow, again with once daily dosing of study drug/medication or placebo. In the first sequence, patients will receive placebo for the first treatment period and BHV-3000 75 mg during the second treatment period. The second sequence will have BHV-3000 75 mg during the first 2 week treatment period, followed by placebo in the second treatment phase.

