### **9.4.2 Primary Endpoint(s)**

The primary endpoint will estimate the effect of rimegepant relative to placebo over 2 weeks of treatment when added to a standard of care therapy, and regardless of the effect of other concomitant medication. The pain score will be the average of the daily 11-point NPRS recorded within each period using the mITT population. This treatment effect will be summarized as the difference in the average daily score in total NPRS between rimegepant and placebo.

The treatment comparison of rimegepant versus placebo will use a two-sided alpha level of 0.05 and a Mixed Model for Repeated Measures (MMRM) that will include fixed effect factors for treatment group, randomization strata (typical/atypical) and sequence, with baseline NPRS as a covariate and subject as a random factor. MMRM-based estimates with corresponding SD, 95% CI, and p-value from MMRM will also be presented.

Observed values and changes from baseline in NPRS will also be summarized using descriptive statistics over time by treatment group.

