2.2 Treatment Assignment

Approximately 120 patients will be screened to randomize 60 patients in a 1:1 ratio into 2 treatment sequences receiving 75 mg rimegepant vs placebo, using a 2-period, 2-sequence, crossover design. Patients with atypical TN and typical TN will be stratified equally into each of the two treatment sequences, with atypical TN patients not exceeding 50 percent of the subjects. Treatment assignments will be obtained by the investigator (or designee) via the Interactive Web-based Response System (IWRS).

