6.3.5.3 S03: Patient Global Impression of Change Scale (PGI-C)

The PGI-C is a patient-rated scale which assesses how the subject's current illness state has improved or worsened relative to the baseline visit. The subject is asked to rate a change in their overall disease condition on a 7-point scale, from 1 ('no change') to 7 ('a great deal better'). The PGI-C is a global index scale that may be used to rate the response of a condition to a therapy.

The PGI-C will be conducted at the beginning and end of each treatment phase as indicated in the Schedule of Assessments.

The PGI-C will be analyzed using the method specified in Section 6.3.2. The MMRM table has the same format as the one described in Section 6.3.2.

6.3.5.4 *S04: Worst Pain Episode*

Using the 11-point NPRS described above, subjects are asked to record an intensity rating of their worst pain episode over a 24-hour period daily in their paper diary.

Worst pain episode score will be analyzed using the same methodology as the primary endpoint (see Section 6.3.4.1) with baseline score as covariate.

6.3.5.5 *S05: ≥ 2 -Point Reduction in the 11 Point NPRS*

Achievement of ≥ 2 -point reduction in average NPRS score will be analyzed using logistic regression, that will include terms for treatment group, randomization strata (typical/atypical), sequence, and baseline NPRS score. See Section 6.3.3 for details. The regression table has the same format as the one described in Section 6.3.3.

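### SAP efficacy models omit the typical/atypical randomisation stratum without explanation, and the responder endpoint S05 has two conflicting model definitions (minor)

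*SAP*

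**What the plan says.** SAP 2.2 describes the allocation: "Patients with atypical TN and typical TN will be stratified equally into each of the two treatment sequences". Protocol 3.5.2 agrees and adds a cap: "patients with atypical TN will not exceed 50% of the subjects".

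Protocol 9.4.2 specifies the primary MMRM with "fixed effect factors for treatment group, randomization strata (typical/atypical) and sequence", plus baseline NPRS and a random subject effect. Protocol 9.4.3 carries the stratum into the continuous secondary endpoints, PGI-C and the 2-point responder model.

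SAP 6.3.1 gives the MMRM as "Fixed effects (categorical variables): treatment group, sequence, and period", with "Covariate (continuous variable): baseline value of dependent variable" and a random subject effect. The primary endpoint is sent there by 6.3.4.1, and S01, S02 and S04 follow the primary method. Sections 6.3.2 (PGI-C) and 6.3.3 (logistic) repeat the same three fixed effects. None of them names the stratum.

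The exception is SAP 6.3.5.5, which describes the S05 logistic model as one "that will include terms for treatment group, randomization strata (typical/atypical), sequence, and baseline NPRS score" and then refers to 6.3.3 for details, where stratum is absent and period is present.

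The SAP states that it is based on protocol version 9.0. It gives no reason for the different terms, and its revision history does not mention them. The Core SAP governs only where this SAP is silent or points to it (SAP 1); on model terms this SAP is explicit.

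**The concern.** A factor used to stratify randomisation normally belongs in the analysis model, and here the protocol says so for every efficacy endpoint. Leaving it out without comment makes the SAP disagree with both the allocation scheme and the protocol. The factor is plausibly prognostic: protocol 1.1 describes atypical disease as more refractory to treatment.

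The S05 conflict is the more concrete defect. Two models are written down for one endpoint, so whoever programs it has to choose.

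At stake are the reported estimates and confidence intervals. SAP 5 states that significance will not be evaluated, so no test or decision rule depends on the term.

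**Working it through.** **Planning figures.** Protocol 9.2 and SAP 5 give a paired-difference SD of 3.8, r = 0.2, 60 randomised, 20% dropout, a 2-point effect and two-sided alpha of 0.05. With 60 × 0.8 = 48 pairs, the noncentrality is (2/3.8)√48 = 3.65 and the noncentral-t power is 94.6%, so the stated power above 90% is reproduced. That calculation contains no stratum term, so the omission does not alter it.

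The implied per-period SD is 3.8/√(2 × 0.8) = 3.00. Hence between-patient variance is 0.2 × 9 = 1.8 and within-patient variance is 0.8 × 9 = 7.2.

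**Treatment difference, both periods observed.** Stratum is constant within a patient and cancels from the within-patient contrast. The SE is 3.8/√60 = 0.491, or 3.8/√48 = 0.548. In simulated trials the estimates with and without stratum differed by less than 1e-14 for stratum gaps of 1, 2 and 3 points.

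**Treatment difference, 20% with period 1 only.** Assumptions: N = 60, equal strata, the gap added to the planning variance, variance components known, 150 simulated trials per setting.

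| Assumed gap | Mean SE without stratum | Mean SE with stratum | Change |
|---|---|---|---|
| 1 point | 0.5286 | 0.5283 | 0.06% |
| 2 points | 0.5309 | 0.5288 | 0.4% |
| 3 points | 0.5332 | 0.5287 | 0.8% |

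In individual simulated trials, including runs at N = 48, the estimate moved by at most about 0.26 points.

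**S05 odds ratio.** The documents give no response rates, so these are assumptions: equal strata, placebo odds centred on 0.3/0.7 = 0.4286, conditional treatment OR of 3, no other covariates.

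- Stratum OR 2: placebo odds are 0.4286 × √2 = 0.606 and 0.4286/√2 = 0.303, giving response rates of 0.377 and 0.233, mean 0.305. Tripling the odds gives 0.645 and 0.476, mean 0.561. The OR from the two means is 2.91.
- Stratum OR 4: placebo odds are 0.857 and 0.214, giving rates of 0.462 and 0.176, mean 0.319. Tripling gives 0.720 and 0.391, mean 0.556. The OR is 2.67.

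**SE of a by-treatment LSMean, N = 60, both periods observed, baseline ignored.** With atypical share p and gap g:

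- Stratum omitted: √[(1.8 + 7.2 + p(1−p)g²)/60].
- Stratum included, strata weighted equally: √[(1.8 + 3.6) × ¼(1/n₁ + 1/n₂) + 7.2/120].
- Stratum included, strata weighted by observed share: √(9/60) = 0.387 at any split.

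| Atypical share | Included, equal weights | Omitted: gap 1 / 2 / 3 |
|---|---|---|
| 50% | 0.387 | 0.393 / 0.408 / 0.433 |
| 30% | 0.409 | 0.392 / 0.405 / 0.426 |
| 20% | 0.448 | 0.391 / 0.401 / 0.417 |

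For example, at 20%: 5.4 × ¼(1/12 + 1/48) + 0.06 = 0.2006, whose root is 0.448. With equal weights, including the stratum raises the SE at every gap for a 20% share, and at gaps 1 and 2 for a 30% share. The documents fix only a 50% cap, and the SAP states no LSMean weighting.

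**The case against.** The strongest reply is that the primary estimand is a within-patient difference, so a between-patient factor hardly touches it. That stands for patients with both periods. The mITT definition asks for a post-baseline assessment in each sequence; since a patient has only one sequence, this presumably means each period, which would exclude most single-period cases. It is not endpoint-specific, so a patient can still lack one Penn-FPS-R, Pain Disability Index or PGI-C visit, but the loss is then of the size shown above.

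A reader might infer that omission always inflates the LSMean standard errors. The documents do not support that: the direction depends on a strata split and a weighting that they do not give. A 3-point gap with equal strata would also need 9/4 = 2.25 of between-patient variance, more than the 1.8 available if the planning SD already includes stratum differences. The baseline covariate may absorb part of any gap as well.

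The change in the S05 odds ratio is non-collapsibility, a move from a conditional towards a marginal quantity, and not bias. That is correct, but the plan should still say which it reports.

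The trial stopped early for low enrolment (SAP 1), so the 60-patient figures are illustrative and a shorter model could be defended. The protocol also calls its statistics section a summary and leaves detail to the SAP. Both points would support a stated departure; neither supplies one, and 6.3.5.5 still keeps the stratum. Adding period suits a crossover and is not at issue.

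Finally, neither S05 list accounts for two records per patient. That is true, but it is a separate matter.

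**Conclusion.** The point holds as a minor one. P01 and S01 to S04 omit the randomisation stratum that the protocol requires, without explanation. For S05 it cannot be said that the stratum is dropped, because the SAP gives two incompatible models.

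A reader might infer that the primary comparison is biased or materially less precise. It is not: there is no change for complete pairs, and about 1% or less in the SE if 20% of patients contribute one period, under the assumed gaps of 1 to 3 points and equal strata. The main numerical consequence is for S05 (3 to 2.91 or 2.67), which rests on assumed stratum odds ratios, response level and equal strata. For the LSMeans no single size or direction can be claimed.

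**What to change.** Add the randomisation stratum, as recorded in IWRS, as a fixed effect in SAP 6.3.1, 6.3.2 and 6.3.3. Naming the source matters because SAP 9.1 anticipates discrepancies between IWRS and CRF type. State that LSMeans are computed at the observed strata margins. Make 6.3.3 and 6.3.5.5 list the same S05 terms: treatment, period, sequence, stratum and baseline NPRS.

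If a shorter model is preferred because of early termination, the SAP should say so, justify the departure from protocol 9.4.2 and 9.4.3, and still leave only one S05 model.

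The cost is one degree of freedom per model and a few lines of text; no new data are needed.
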